| Sub-study Screened | 
 • Comprised of all subjects screened for inclusion in the sub-study. • All screened subjects will continue using their subject numbers received in the main study. | 
 • Study Population |
| Sub-study Safety | 
 • All randomized subjects who received at least one CAB and/or RPV thigh injection. • Subjects will be assessed according to actual treatment received. | 
 • Safety • Virology |
| Sub-study ITT-E | 
 • All randomized subjects who received at least one CAB and/or RPV thigh injection. • Subjects will be assessed according to their randomized treatment, regardless of the treatment they received. | 
 • Study Population • Efficacy • Health Outcomes |
| Sub-study PK Concentration | 
 • All subjects who received at least one CAB and/or RPV thigh injection and provided at least one non-missing CAB and/or RPV plasma concentration value (non-quantifiable values will be considered as non-missing values) during the sub-study. | 
 • PK |
| Sub-study PK Parameter | 
 • All subjects who received at least one CAB and/or RPV thigh injection and had at least one evaluable PK parameter estimate during the sub-study. | 
 • PK |
| Sub-study CVF | 
 • All subjects receiving at least one CAB and/or RPV thigh injection who met Confirmed Virologic Failure (CVF) criteria in the sub-study. | 
 • Virology • Efficacy |

| Population | Definition / Criteria | Analyses Evaluated |
|----------------|---|--|
| Sub-study LTFU | 
 • All subjects receiving at least one CAB and/or RPV thigh injection who have discontinued the CAB LA + RPV LA regimen and have either at least one Long-term Follow-up phase clinic visit (i.e. have at least one long-term follow-up visit shown in the study database, LTFU month 1, LTFU month 3, etc) or have filled out the LTFU phase conclusion form or have indicated the continuation to LTFU phase in the subject continuation form. | 
 • Study Population |

Refer to Section [15.15](#): List of Data Displays which details the population used for each display.

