| Extension | 
For participants continuing into Extension Phase and not entering the sub-study:
 
If participants continued into LTFU Phase after the Extension phase: Date of Nominal Week 100 Visit \leq Date $<$ LTFU ART Start Date^[a]
 
If participants transitioned to marketed product/alternative HAART and did not withdraw study due to safety related reason, then
 
Date of Nominal Week 100 Visit^[a] \leq Date $<$ Date of end of study +35 days (Q4W) or + 63 days (Q8W)
 
For participants continuing into Extension Phase, entering the sub-study but not returning to Extension Phase:
 
Date of Nominal Week 100 Visit \leq Date $<$ Date of First Sub-study Record
 
For participants continuing into Extension Phase, entering the sub-study and returning to Extension Phase:
 
Before the sub-study: Date of Nominal Week 100 Visit \leq Date $<$ Date of First Sub-study Record
 
After the sub-study:
 
For participants continuing into LTFU Phase after return to extension phase:
 
End of Sub-study Date^[b] $<$ Date $<$ LTFU ART Start Date^[a]
 
For participants transitioned to marketed product/alternative HAART and did not withdraw study due to safety related reason:
 
End of Sub-study Date^[b] $<$ Date $<$ Date of end of study +35 days (Q4W) or + 63 days (Q8W)
 |
| Sub-study Screening | 
For participants entering the sub-study and not receiving any thigh injection:
 
If participants continued into LTFU Phase after the sub-study, then
 
Date of First sub-study record \leq Date $<$ LTFU ART Start Date^[a]
 
If participants transitioned to marketed product/alternative HAART and did not withdraw study due to safety related reason, then
 
Date of First sub-study record \leq Date $<$ Date of end of study +35 days (Q4W) or + 63 days (Q8W)
 
If participants continued into Extension Phase after the sub-study, then
 
Date of First sub-study record \leq Date \leq End of Sub-study Date^[b]
 
For participants entering the sub-study and receiving thigh injection(s):
 
Date of First sub-study record \leq Date $<$ Date of First Thigh Injection
 |

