| 2.19 | 2.19 | NA | Intent-to-Treat Exposed | Shell EFF_T1 | Summary of Kaplan-Meier Estimates of Proportion of Subjects Without Confirmed Virologic Failure at Week 48 - Treatment Related Discontinuation = Failure | Adjust the row labels and footnotes as appropriate. For WK96, replace 'Week 48' with 'Week96' in title. | W48, W96 | |
| 2.20 | 2.20 | NA | Intent-to-Treat Exposed | Shell EFF_T2 | Summary of Kaplan-Meier Estimates of Proportion of Subjects Without Confirmed Virologic Failure at Week 48 - Efficacy Related Discontinuation = Failure | Adjust the row labels and footnotes as appropriate. For WK96, replace 'Week 48' with 'Week96' in title. | W48, W96 | |

CONFIDENTIAL

207966

| Efficacy Tables | | | | | | | | |
|-----------------|------------|------------|-----------------------------|-------------------------|--|--|-------------------|--|
| No. in W48 | No. in W96 | No. in EOS | Population | IDSL / Example Shell | Title | Programming Notes | Deliverable | |
| 2.21 | 2.21 | NA | Intent-to-Treat Exposed | 201585/primary_02/T2.19 | Proportion of Subjects with HIV-1 RNA >=50 c/mL at Week 48 (Snapshot) by Last Delay in IP Injection (Maintenance Phase) | Display both arms. Change the footnote to 'The last delay in IP injection will be the delay in IP injection at Week 48, or the delay in last IP injection prior to Week 48 if a participant did not receive Week 48 injection (i.e. missing visit or withdrawal)'. For WK96, replace 'Week 48' with 'Week 96' in the title and footnote accordingly. | W48, W96 | |
| 2.22 | 2.22 | 2.1 | Intent-to-Treat Exposed | 201585/primary_02/T2.20 | Summary of Plasma HIV-1 RNA (log10 c/mL) by Visit (Maintenance + Extension Phase) | | W48, W96, EOS | |
| 2.23 | 2.23 | NA | Intent-to-Treat Exposed | 201585/primary_02/T2.21 | Cumulative Proportion of Subjects Meeting Confirmed Virology Failure Criteria by Visit during the Maintenance Phase (Up to Week 48) | For WK96, remove 'Up to Week 48' in title. | HL, W48, W96 | |
| 2.24 | 2.24 | 2.2 | Intent-to-Treat Exposed | 201584/primary_01/T2.21 | Cumulative Proportion of Subjects Meeting Confirmed Virology Failure Criteria (Maintenance + Extension Phase) | | HL, W48, W96, EOS | |
| 2.25 | 2.25 | NA | Confirmed Virologic Failure | 201584/primary_01/T2.24 | Distribution of Quantitative Plasma HIV-1 RNA Results at Suspected and Confirmation of Confirmed Virologic Failure (Maintenance Phase) | | W48, W96 | |

| Efficacy Tables | | | | | | | | |

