| 3.6 | 3.7 | NA | Safety | 201585/primary_02/T3.8 | Summary of All Adverse Events by System Organ Class and Maximum Toxicity (Maintenance Phase) | | HL, W48, W96 | |
| NA | 3.8 | 3.3 | Safety | 201585/primary_02/T3.8 | Summary of All Adverse Events by System Organ Class and Maximum Toxicity (Maintenance + Extension Phase) | | W96, EOS | |
| 3.7 | 3.9 | NA | Safety | 201585/primary_02/T3.8 | Summary of All Adverse Events Excluding Study Drug Injection Site Reactions by System Organ Class and Maximum Toxicity (Maintenance Phase) | | HL, W48, W96 | |
| NA | NA | 3.4 | Safety | 201585/primary_02/T3.8 | Summary of All Adverse Events Excluding Study Drug Injection Site Reactions by System Organ Class and Maximum Toxicity (Maintenance + Extension Phase) | | EOS | |
| NA | NA | 3.5 | Long-term Follow-up | 201585/primary_02/T3.8 | Summary of All Adverse Events by System Organ Class and Maximum Toxicity (Long-term Follow-up Phase) | | EOS | |
| 3.8 | 3.10 | NA | Safety | 201585/primary | Summary of All On-treatment Adverse | | W48, W96 | |

CONFIDENTIAL

207966

| Safety Tables | | | | | | | | |
|---------------|------------|------------|--------------|--------------------------|---|---|--------------|--|
| No. in W48 | No. in W96 | No. in EOS | Population | IDSL / Example Shell | Title | Programming Notes | Deliverable | |
| | | | | y_02/T3.11 | Events by System Organ Class and Maximum Toxicity (Maintenance Phase) | | | |
| 3.9 | NA | NA | Oral Lead-in | 201585/primary_02/T3.13 | Summary of All Adverse Events by System Organ Class and Maximum Toxicity (Oral Lead-in Period during the Maintenance Phase) | Remove the footnote. Display both arms. | W48 | |
| 3.10 | 3.11 | NA | Safety | 201585/primary_02/T3.14 | Summary of Common Adverse Events (>=5%) by Overall Frequency (Maintenance Phase) | | W48, W96 | |
| 3.11 | 3.12 | NA | Safety | 201585/primary_02/T3.15 | Summary of Common Grade 2-5 Adverse Events (>=1%) by Overall Frequency (Maintenance Phase) | | W48, W96 | |
| 3.12 | 3.13 | NA | Safety | 201585/primary_02/T3.16 | Summary of All Drug-related Adverse Events by System Organ Class (Maintenance Phase) | | W48, W96 | |
| 3.13 | 3.14 | NA | Safety | 201585/primary_02/T3.17 | Summary of All Drug-related Adverse Events by System Organ Class and Maximum Toxicity (Maintenance Phase) | | HL, W48, W96 | |

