| NA | 3.15 | 3.6 | Safety | 201585/primary_02/T3.17 | Summary of All Drug-related Adverse Events by System Organ Class and Maximum Toxicity (Maintenance + Extension Phase) | | W96, EOS | |
| 3.14 | 3.16 | NA | Safety | 201585/primary_02/T3.101 | Summary of All Drug-related Adverse Events Excluding Study Drug Injection Site Reactions by System Organ Class and Maximum Toxicity (Maintenance Phase) | | HL, W48, W96 | |
| NA | NA | 3.7 | Safety | 201585/primary | Summary of All Drug-related Adverse | | EOS | |

| Safety Tables | | | | | | | | |
|--|------------|------------|---------------------|-------------------------|---|--------------------|---------------|--|
| No. in W48 | No. in W96 | No. in EOS | Population | IDSL / Example Shell | Title | Programming Notes | Deliverable | |
| | | | | y_02/T3.101 | Events Excluding Study Drug Injection Site Reactions by System Organ Class and Maximum Toxicity (Maintenance + Extension Phase) | | | |
| 3.15 | 3.17 | NA | Safety | 201585/primary_02/T3.20 | Summary of All Drug-Related Grade 2-5 Adverse Events by Overall Frequency (Maintenance Phase) | | W48, W96 | |
| Serious and Other Significant Adverse Events | | | | | | | | |
| 3.16 | 3.18 | NA | Safety | 201585/primary_02/T3.21 | Summary of Serious Adverse Events by System Organ Class (Maintenance Phase) | | HL, W48, W96 | |
| NA | 3.19 | 3.8 | Safety | 201585/primary_02/T3.21 | Summary of Serious Adverse Events by System Organ Class (Maintenance + Extension Phase) | | W96, EOS | |
| 3.17 | 3.20 | 3.9 | Long-term Follow-up | 201585/primary_02/T3.24 | Summary of Serious Adverse Events by System Organ Class (Long-term Follow-up Phase) | | W48, W96, EOS | |
| 3.18 | NA | NA | Oral Lead-in | 201585/primary_02/T3.25 | Summary of Serious Adverse Events by System Organ Class (Oral Lead-in Period during the Maintenance Phase) | Display both arms. | W48 | |
| 3.19 | 3.21 | NA | Safety | 201585/primary_02/T3.26 | Summary of Drug-related Serious Adverse Events by System Organ Class (Maintenance Phase) | | W48, W96 | |
| NA | 3.22 | 3.10 | Safety | 201585/primary_02/T3.26 | Summary of Drug-related Serious Adverse Events by System Organ Class (Maintenance + Extension Phase) | | W96, EOS | |
| 3.20 | 3.23 | NA | Safety | 201585/primary_02/T3.29 | Summary of Non-Fatal Serious Adverse Events by Overall Frequency (Maintenance | | W48, W96 | |

CONFIDENTIAL

207966

| Safety Tables | | | | | | | | |

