|---------------|------------|------------|--------------|-------------------------|---|---|--------------|--|
| No. in W48 | No. in W96 | No. in EOS | Population | IDSL / Example Shell | Title | Programming Notes | Deliverable | |
| | | | | | Phase) | | | |
| 3.21 | 3.24 | NA | Safety | 201585/primary_02/T3.30 | Summary of Drug-related Non-Fatal Serious Adverse Events by Overall Frequency (Maintenance Phase) | | W48, W96 | |
| 3.22 | 3.25 | NA | Safety | 201585/primary_02/T3.31 | Summary of Adverse Events Leading to Withdrawal/Permanent Discontinuation of Investigational Product by System Organ Class (Maintenance Phase) | | HL, W48, W96 | |
| NA | 3.26 | 3.11 | Safety | 201585/primary_02/T3.31 | Summary of Adverse Events Leading to Withdrawal/Permanent Discontinuation of Investigational Product by System Organ Class (Maintenance + Extension Phase) | | W96, EOS | |
| 3.23 | NA | NA | Oral Lead-in | 201585/primary_02/T3.34 | Summary of Adverse Events Leading to Withdrawal/Permanent Discontinuation of Investigational Product by System Organ Class (Oral Lead-in Period during the Maintenance Phase) | Remove the footnote. Display both arms. | W48 | |
| 3.24 | 3.27 | NA | Safety | 201585/primary_02/T3.35 | Summary of Common (>=5%) Non-Serious Adverse Events (Maintenance Phase) | | W48, W96 | |
| 3.25 | 3.28 | NA | Safety | 201585/primary_02/T3.36 | Summary of Subjects and Number of Occurrences of Common (>=5%) Non-Serious Adverse Events by System Organ Class (Maintenance Phase) | | W48, W96 | |
| 3.26 | 3.29 | NA | Safety | 201585/primary_02/T3.37 | Summary of Subjects and Number of occurrences of SAEs, Fatal SAEs, and Drug-related SAEs (Maintenance Phase) | | W48, W96 | |
| 3.27 | 3.30 | NA | Safety | 201585/primary | Summary of Cumulative Adverse Events | Note that this table only display AEs | W48, W96 | |

| Safety Tables | | | | | | | | |
|---|------------|------------|------------|-------------------------|--|--|--------------|--|
| No. in W48 | No. in W96 | No. in EOS | Population | IDSL / Example Shell | Title | Programming Notes | Deliverable | |
| | | | | y_02/T3.38 | by Visit (Maintenance Phase) | occurring >=5% subjects during Maintenance Phase. | | |
| Study Drug Injection Site Reaction Adverse Events (display for both arms) | | | | | | | | |
| 3.28 | 3.31 | NA | Safety | 201585/primary_02/T3.40 | Summary of Study Drug Injection Site Reaction Adverse Events (Event-level Summary) - Maintenance Phase | | HL, W48, W96 | |

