| 15 | 15 | 15 | Safety | 201585/primary_02/L15 | Listing of Fatal Adverse Events (Maintenance + Extension Phase) | Add Study Period to the 5 th Column from the left. For WK96 and EOS: Remove "(Maintenance + Extension Phase)" from the title (i.e. no phase restriction). | W48, W96, EOS |

CONFIDENTIAL

207966

| ICH Listings | | | | | | | |
|--------------------------|------------|------------|------------|-----------------------|--|--|-------------------|
| No. in W48 | No. in W96 | No. in EOS | Population | IDS / Example Shell | Title | Programming Notes | Deliverable |
| 16 | 16 | 16 | Safety | 201585/primary_02/L16 | Listing of Non-Fatal Serious Adverse Events (Maintenance + Extension Phase) | Add Study Period to the 5 th Column from the left. For WK96 and EOS: Remove "(Maintenance + Extension Phase)" from the title (i.e. no phase restriction). | W48, W96, EOS |
| 17 | 17 | 17 | Safety | 201585/primary_02/L17 | Listing of Adverse Events Leading to Withdrawal/Permanent Discontinuation of Investigational Product (Maintenance + Extension Phase) | Add Study Period to the 5 th Column from the left. | HL, W48, W96, EOS |
| 18 | 18 | 18 | Safety | 201585/primary_02/L18 | Listing of Changes in Intensity/Grades of Study Drug Injection Site Adverse Events (Maintenance + Extension Phase) | For WK96 and EOS: Remove "(Maintenance + Extension Phase)" from the title (i.e. no phase restriction). | W48, W96, EOS |
| 19 | 19 | 19 | Safety | 201585/primary_03/L30 | Listing of All Adverse Events (Maintenance + Extension Phase) | Add Study Period to the 5 th Column from the left. For WK96 and EOS: Remove "(Maintenance + Extension Phase)" from the title (i.e. no phase restriction). | W48, W96, EOS |
| NA | 66 | 66 | Safety | 207966/primary_02/L19 | Listing of COVID-19 Adverse Events | | W96, EOS |
| NA | 67 | 67 | Safety | SAF_L1 | Listing of COVID-19 Assessments | | W96, EOS |
| NA | 68 | 68 | Safety | SAF_L2 | Listing of COVID-19 Symptoms | | W96, EOS |
| Safety: Pregnancy | | | | | | | |
| 20 | 20 | 20 | Safety | 201585/primary_02/L19 | Listing of Subjects Who Became Pregnant during the Study (Maintenance + Extension Phase) | For EOS, remove "(Maintenance + Extension Phase)" from the title. | W48, W96, EOS |

CONFIDENTIAL

207966

| ICH Listings | | | | | | | |
|--------------------------------------|------------|------------|------------|-----------------------|---|---|---------------|

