| 3.6 | Sub-study Safety | 207966/primary_34/T3.6 | Summary of All Adverse Events by System Organ Class and Maximum Toxicity (Thigh Injection Phase) | | Sub-study |
| 3.7 | Sub-study Safety | 207966/primary_34/T3.6 | Summary of All Adverse Events by System Organ Class and Maximum Toxicity (Thigh Injection + Return to Gluteal Injection Phase) | | Sub-study |
| 3.8 | Sub-study Safety | 207966/primary_34/T3.8 | Summary of All Adverse Events Excluding Study Drug Injection Site Reactions by System Organ Class and Maximum Toxicity (Thigh Injection Phase) | | Sub-study |
| 3.9 | Sub-study Safety | 207966/primary_34/T3.10 | Summary of Common Adverse Events (>=5%) by Overall Frequency (Thigh Injection Phase) | | Sub-study |
| 3.10 | Sub-study Safety | 207966/primary_34/T3.11 | Summary of Common Grade 2-5 Adverse Events (>=1%) by Overall Frequency (Thigh Injection Phase) | | Sub-study |
| 3.11 | Sub-study Safety | 207966/primary_34/T3.13 | Summary of All Drug-related Adverse Events by System Organ Class and Maximum Toxicity (Thigh Injection Phase) | | Sub-study |

| Safety Tables | | | | | |
|--|------------------|-------------------------|--|----------------------|-------------|
| No. | Population | IDSL / Example Shell | Title | Programming Notes | Deliverable |
| 3.12 | Sub-study Safety | 207966/primary_34/T3.15 | Summary of All Drug-related Adverse Events Excluding Study Drug Injection Site Reactions by System Organ Class and Maximum Toxicity (Thigh Injection Phase) | | Sub-study |
| 3.13 | Sub-study Safety | 207966/primary_34/T3.16 | Summary of All Drug-Related Grade 2-5 Adverse Events by Overall Frequency (Thigh Injection Phase) | | Sub-study |
| Serious and Other Significant Adverse Events | | | | | |
| 3.14 | Sub-study Safety | 207966/primary_34/T3.17 | Summary of Serious Adverse Events by System Organ Class (Thigh Injection Phase) | | Sub-study |
| 3.15 | Sub-study Safety | 207966/primary_34/T3.17 | Summary of Serious Adverse Events by System Organ Class (Thigh Injection +Return to Gluteal Injection Phase) | | Sub-study |
| 3.16 | Sub-study Safety | 207966/primary_34/T3.19 | Summary of Drug-related Serious Adverse Events by System Organ Class (Thigh Injection Phase) | | Sub-study |
| 3.17 | Sub-study Safety | 207966/primary_34/T3.22 | Summary of Adverse Events Leading to Withdrawal/Permanent Discontinuation of Investigational Product or Withdrawal from Study by System Organ Class (Thigh Injection Phase) | Remove the footnote. | Sub-study |

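### Adverse events and virologic failures in Sub-study Screening fall between the end-of-study tables and the sub-study tables, and end-of-study exposure covers a different period from the events

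*SAP*

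**What the plan says.** Section 15.4.1 assigns each event to a phase. For sub-study entrants, Table 17 (AEs) and Table 18 (laboratory data, including HIV-1 RNA) close the Extension Phase before the first sub-study record. For those who return, Extension reopens after the End of Sub-study Date. The time between is split into Sub-study Screening, Thigh Injection and Return to Gluteal Injection. Sub-study Screening has its own rule for the group described as "For participants entering the sub-study and not receiving any thigh injection".

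The EOS displays in Section 15.15.5 use the two main-study phases:
- Table 3.3: "Summary of All Adverse Events by System Organ Class and Maximum Toxicity (Maintenance + Extension Phase"
- Table 3.8: "Summary of Serious Adverse Events by System Organ Class (Maintenance + Extension Phase"
- Table 3.11: "Summary of Adverse Events Leading to Withdrawal/Permanent Discontinuation of Investigational Product by System Organ Class (Maintenance + Extension Phase"
- Table 2.2: "Cumulative Proportion of Subjects Meeting Confirmed Virology Failure Criteria (Maintenance + Extension Phase"
- Listing 17: "Listing of Adverse Events Leading to Withdrawal/Permanent Discontinuation of Investigational Product (Maintenance + Extension Phase"

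The EOS tables for injection site reactions, AEs of special interest and disease progression or death carry the same restriction. No programming note adds the sub-study phases.

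The sub-study displays in Section 15.15.7 begin at the first thigh injection, for example Table 3.15: "Summary of Serious Adverse Events by System Organ Class (Thigh Injection +Return to Gluteal Injection Phase". They use the Sub-study Safety population, defined in Section 4 as "All randomized subjects who received at least one CAB and/or RPV thigh injection".

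**The concern.** The EOS titles are shared with the Week 96 analysis. Sub-study entry requires at least 152 weeks in the main study (Section 2.3), so at Week 96 Maintenance plus Extension covered all on-treatment time. At EOS it no longer does, and the titles were not adapted.

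The EOS tables are the cumulative safety record of the two randomised regimens. Sub-study Screening is a continuation of those regimens: the injection site and frequency are unchanged. An SAE in that period in a participant who stays on treatment would be listed but not counted in any on-treatment SAE table. The untabulated window is planned to be twice as long per participant in Q8W as in Q4W, so the omission is not symmetric between the arms being compared.

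**Working it through.** **Where an event is counted.** The phase rules set against the table titles give:

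| Phase of the event | EOS Maintenance + Extension tables | Sub-study tables (15.15.7) |
|---|---|---|
| Extension, before the first sub-study record | yes | no |
| Sub-study Screening | no | no, for all AEs, SAEs, AEs leading to withdrawal, and CVF |
| Thigh Injection | no | yes |
| Return to Gluteal | no | yes |
| Extension, after the End of Sub-study Date | yes | no |

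For CVF, EOS Table 2.2 covers Maintenance + Extension and sub-study Table 2.9 covers Thigh + Return to Gluteal. The Sub-study CVF population requires a thigh injection. A CVF in Sub-study Screening meets none of these.

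**What still catches a Sub-study Screening event.**
- EOS Listings 13-16, 18 and 19 drop the phase restriction, so the event is listed.
- EOS Tables 1.3 (study conclusion) and 1.9 (study drug discontinuation) have no phase limit. They count a participant who stops, but do not tabulate AE terms by system organ class.
- EOS Tables 3.5 (all AEs) and 3.9 (SAEs) cover Long-term Follow-up (LTFU). Table 19 starts LTFU after the last injection or oral bridging, and Section 15.4.1 lets it overlap Sub-study Screening. Events after the last injection count there if the participant meets the LTFU population definition.
- EOS Figure 2.1 and Listing 41 show CVF participants with no phase limit in the title.
- Sub-study Table 3.23 (injection site reactions by visit) may include Screening reactions, but only in participants who later had a thigh injection.

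**Size.** Section 2.3 gives 41 participants per arm, Screening of 4 weeks (Q4W) or 8 weeks (Q8W), 16 weeks of thigh injections and 8 weeks of return to gluteal. The plan states no figure of its own to reproduce.
- Screening: 41 × 4 + 41 × 8 = 164 + 328 = 492 weeks; 492 × 7 / 365.25 = 9.4 person-years. The Q8W share is 328 / 492 = 67%.
- Thigh Injection: 82 × 16 = 1,312 weeks = 25.1 person-years.
- Return to Gluteal: 82 × 8 = 656 weeks = 12.6 person-years.
- Total outside the EOS Maintenance + Extension tables: 492 + 1,312 + 656 = 2,460 weeks = 47.1 person-years. The part also missing from the sub-study tables is 492 / 2,460 = 20%.

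**Exposure.** In Section 15.6.4, EOS overall exposure runs from first dose to the latest Maintenance/Extension visit, with no deduction for the sub-study. The injection count covers only Maintenance and Extension. Take a participant who completes the sub-study and returns to Extension:
- Q4W: 4 + 16 + 8 = 28 weeks are included in exposure. The schedule in Section 15.2.3 has 7 injection visits in that time (Weeks -4, 0, 4, 8, 12, 16 and 20).
- Q8W: 8 + 16 + 8 = 32 weeks are included. Section 15.2.4 has 4 injection visits (Weeks -8, 0, 8 and 16).

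Week 0 is Sub-study Day 1, and the Week 24 injection belongs to the main study. Treating the Screening injection as a sub-study injection, none of these visits enters the EOS injection count and none of the events in those weeks enters the EOS event tables, yet the weeks are in the exposure.

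**The case against.** A reader might infer that every adverse event and virologic failure of the sub-study is lost, some 47 person-years. The SAP does not support that. Four fifths of that time is Thigh Injection and Return to Gluteal, whose AEs, SAEs, AE withdrawals and CVFs have their own tables in Section 15.15.7. Nor do the EOS tables cover only Maintenance and Extension: Tables 3.5 and 3.9 cover LTFU, Tables 1.3 and 1.9 count stopping in any phase, and most AE listings are unrestricted. CVF is a matter of the efficacy and virology displays, not the safety tables.

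The gap is also shorter for screen failures. Section 15.6.1 sets their End of Sub-study Date at the date they fail eligibility, so those who continue resume Extension from then. Against an illustrative 1,020 × 152 = 155,040 participant-weeks without dropout, 492 weeks is 0.3%. None of the EOS tables cited divides events by exposure. Keeping thigh-injection events apart from the main Q8W versus Q4W tables is a defensible choice, because the injection site differs.

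These points narrow the concern but leave its core. The injection-site argument does not apply to Sub-study Screening, which is gluteal. The LTFU tables do not reach participants who keep dosing, and participants who move to marketed product generally skip LTFU. The LTFU population also needs a visit, a phase conclusion form or a continuation record, which a participant who dies in Screening may not have. Listing 17 keeps its phase limit although its neighbours dropped theirs.

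**Conclusion.** The point holds in this limited form. Read as written, the SAP leaves on-treatment Sub-study Screening events out of every on-treatment all-AE, SAE and AE-leading-to-withdrawal table, and leaves a CVF in that phase out of every CVF table. The planned size is about 9.4 person-years, assuming 41 per arm, the full planned Screening length and no early withdrawal; time from screen failures is not included. How many events fall there cannot be known from the plan.

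Thigh Injection and Return to Gluteal events are absent from the EOS cumulative tables but not from reporting. Whether to pool them is a choice the SAP should state, and it does not. The exposure mismatch is real for participants who return to Extension. It matters most if the participant-years derived in Section 15.6.4 are set against the EOS event counts. The Week 48 primary and key secondary analyses precede the sub-study and are unaffected.

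**What to change.** 1. Include Sub-study Screening in the EOS cumulative displays of AEs, SAEs, AEs leading to discontinuation, AEs of special interest, injection site reactions, CVF and disease progression or death, and say so in the titles.
2. Remove the phase restriction from Listing 17, as was done for Listings 13-16, 18 and 19.
3. Compute EOS overall exposure and injection counts over the same phases as the event tables.
4. For Thigh Injection and Return to Gluteal, either add a supplementary all-phases EOS count of SAEs, deaths, AE discontinuations and CVF, or state in a footnote that these phases are excluded and reported in Section 15.15.7.

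The cost is SAP wording, a phase filter and an exposure derivation in existing programs. No additional data collection is needed.
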